3.7.3 Off Protocol Therapy and Off Study Procedure

Authorized staff must notify Central Registration Office (CRO) when a subject is taken off protocol therapy and when a subject is taken off study.

- NCI site: Complete the Participant Status Updates Form available from the web site (<http://home.ccr.cancer.gov/intra/eligibility/welcome.htm>) main page. Hand deliver the completed form to the BTTC Coordinating Center Research Nurse or send via encrypted email.
- Participating sites: The Participant Status Update Form will be supplied by the BTTC Coordinating Center's Research Nurse. Sites will send the completed form by secure fax to [contact] or by secure email (NIH Secure Email and File Transfer Service [SEFT]).
- BTTC Coordinating Center: The BTTC Research Nurse will review the Participant Status Updates Form and forward to the Central Registration Office (CRO).

4.0 CONCOMITANT MEDICATIONS/MEASURES

- 4.1.1 G-CSF Administration: Routine prophylactic use of G-CSF is not permitted. However, therapeutic use in patients with serious neutropenic complications, such as sepsis, may be considered at the investigator's discretion.
- 4.1.2 Corticosteroids should be used in the smallest dose to control symptoms of cerebral edema and mass effect, and discontinued if possible. Patients must not be on a dexamethasone dose of greater than 16 mg/ day.
- 4.1.3 Anti-seizure medications should be used as indicated. If for unavoidable clinical reasons (severe allergies, toxicities etc.) a patient's AED is switched to the alternate AED group the following guidelines must be followed:

EVERY EFFORT SHOULD BE MADE TO MAINTAIN THE PATIENT ON NON-EIAED

Patients, who were previously on a non-EIAED and need to change anticonvulsants, should be started on another non-EIAED if at all possible. No delays in treatment would be required.

Patients who were previously on a non- EIAED and were inadvertently and temporarily changed to an EIAED, should immediately be started on another non-EIAED. The patient may continue the current treatment dose while a non- EIAED is re-started.

Patients who were previously on a non-EIAED and need to permanently change anticonvulsant, but who cannot change to another non-EIAED may continue the current treatment dose for the next 2 weeks while an EIAED is started. FOLLOWING

THIS 2 WEEK PERIOD, THE SUBSEQUENT TREATMENT DOSE MUST BE DISCUSSED WITH THE STUDY CHAIR. In some cases this dose may be higher than the previously used dose.

- 4.1.4 Febrile neutropenia may be managed according to the local institution's Infectious Disease guidelines. Measures may include appropriate laboratory testing, including blood and urine cultures and the institution of broad-spectrum antibiotics. If a source for the fever is not identified or the fever resolves when the neutrophil count recovers, antibiotics may be discontinued and the patient observed.
- 4.1.5 Antiemetics: The use of antiemetics will be left to the investigators' discretion.
- 4.1.6 Other Concomitant Medications: Therapies considered necessary for the well-being of the patient may be given at the discretion of the investigator. Other concomitant medications should be avoided except for analgesics, chronic treatments for concomitant medical conditions, or agents required for life-threatening medical problems. All concomitant medications must be recorded.
- 4.1.7 Other Anticancer or Experimental Therapies: No other anticancer therapy (including chemotherapy, radiation, hormonal treatment or immunotherapy) of any kind is permitted during the study period. No other drug under investigation may be used concomitantly with the study drug.
- 4.1.8 Surgery: If neurosurgical management is required for reasons not due to tumor progression, these procedures must be documented, including the indications for surgery, the surgical operative note and pathology report. If possible, defer surgery for 4 weeks from last dose of therapy. Patients who undergo resection for presumed tumor

progression but are shown to only have treatment associated changes can resume treatment once they have recovered from the surgical procedure. Everolimus treatment can only resume > 1 week after surgery.

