3.7 CRITERIA FOR REMOVAL FROM PROTOCOL THERAPY AND OFF STUDY CRITERIA

3.7.1 Criteria for Removal from Protocol Therapy:

3.7.1.1 Progression of disease (as defined in Section 5.2.1).

Patients must be followed by the same type of brain scan, as was used for baseline tumor measurements, and will be removed from study if progression is documented after any cycle of treatment. Patients with stable disease, partial or complete response will continue on therapy as defined in Section 3.0.

3.7.1.2 Unacceptable toxicity (as defined by the investigator).

3.7.1.3 The patient may withdraw from the study at any time for any reason.

3.7.1.4 Medical or psychiatric illness which in the investigator's judgment renders the patient incapable of further therapy.

3.7.1.5 Treatment delay due to toxicity greater than 21 days measured from the start of the preceding cycle.

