5.2.1.3.1 Complete Response (CR)

Complete disappearance of all CE measurable and evaluable disease. No new lesions. No evidence of non-evaluable disease. All measurable, evaluable and non-evaluable lesions and sites must be assessed using the same techniques as baseline. Patients must be on no steroids. There must be stable or improved non-enhancing (T2/FLAIR) lesions. Stable or improved clinically. Note: Patients with non-measurable disease cannot have a partial response. The best possible response is stable disease.

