5.2.1.3.2 Partial Response (PR)

Greater than or equal to 50% decrease under baseline in the sum of products of perpendicular diameters of the two largest CE measurable lesions, sustained for at least 4 weeks. In the absence of a confirming scan 4 weeks later, this scan will be considered only stable disease. If more than two clearly defined lesions exist, the remaining lesions will be considered as evaluable. No progression of evaluable or non-measurable disease. No new lesions. All measurable and evaluable lesions and sites must be assessed using the same techniques as baseline. The steroid dose at the time of the scan evaluation should be no greater than the maximum dose used in the first 8 weeks from initiation of therapy. Stable or improved non-enhancing (T2/FLAIR) lesions on same or lower dose of corticosteroids compared to baseline. Stable or improved clinically. Note: Patients with non-measurable disease cannot have a partial response. The best response possible is stable disease.

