5.2.1.3.5 Progression

- a. >25% increase in the sum of products of perpendicular diameters of enhancing lesions (over baseline if no decrease) on stable or increasing dose of corticosteroids.
and/or
- b. Significant increase in T2/FLAIR non-enhancing lesion on stable or increasing doses of corticosteroids compared to baseline scan or best response following initiation or therapy, not due to co-morbid events (radiation therapy, demyelination, ischemic injury, infection, seizures, postoperative changes, or other treatment effects).
- c. Any new lesion
- d. Clear clinical deterioration not attributable to other causes apart from the tumor (e.g., seizures, medication side effects, complications of therapy, cerebrovascular events, infection, etc.). The definition of clinical deterioration is left to the discretion of the treating physician, but it is recommended that a decrease in 20% of KPS or from any baseline to 50% or less be considered, unless attributable to comorbid events.
- e. Failure to return for evaluation due to death or deteriorating condition.

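### Progression criteria (a) and (c) have no exception for pathology-proven treatment change, although 4.1.8 lets such patients resume treatment, and the response rules do not exclude shrinkage caused by surgery

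*Combined protocol and SAP*

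**What the plan says.** **Surgery.** Section 4.1.8 allows a patient who undergoes resection for presumed tumour "progression but are shown to only have treatment associated changes can resume treatment once they have recovered from the surgical procedure". It does not say how the scan that led to surgery, or the scans after it, are scored.

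**Progression.** In 5.2.1.3.5, criterion (a) is a ">25% increase in the sum of products of perpendicular diameters of enhancing lesions" on stable or increasing steroids, and criterion (c) is any new lesion. Neither mentions treatment effect or pathology. Criterion (b), on T2/FLAIR, does: it sets aside growth due to "postoperative changes, or other treatment effects", among other causes. Criterion (d), on clinical decline, sets aside causes other than the tumour.

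**Removal.** Under 3.7.1.1 a patient "will be removed from study if progression is documented after any cycle of treatment". No exception refers to 4.1.8.

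**Response.** PR (5.2.1.3.2) starts from "Greater than or equal to 50% decrease under baseline in the sum of products of perpendicular diameters of the two largest CE measurable lesions". CR (5.2.1.3.1) starts from "Complete disappearance of all CE measurable and evaluable disease". Best response (5.2.2) is derived from the sequence of objective statuses. None of the three mentions surgery, and no new reference scan after an operation is defined.

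**The concern.** The plan foresees a particular event, decides what it means for treatment, and leaves the endpoint definitions to say something else. A patient who meets (a) or (c), and whose resection then shows only treatment-associated change, is a progression event under 5.2.1.3.5, is due for removal under 3.7.1.1, and may continue under 4.1.8. The primary endpoint would then count as a failure a progression that pathology has refuted.

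The second gap runs the other way. If that scan is set aside, the post-operative scan is compared with a pre-operative baseline, and tissue taken out by the surgeon can appear as a drug response. The first sentence of 4.1.8 also anticipates neurosurgery for reasons other than progression, so this exposure is not limited to refuted progressions.

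The cohorts are small and their cut-offs are low (9 of 34, and 2 of 32), so single patients can matter.

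**Working it through.** **1. Literal scoring of an illustrative patient** (areas are hypothetical)
- Baseline 8 cm²; week 8, 11 cm² on stable steroids. Change = 11/8 − 1 = +37.5%. This exceeds 25%, so (a) is met. Pathology later shows treatment change only; nothing in (a) reverses the call.
- Post-operative area 1 cm². Change from baseline = 1/8 − 1 = −87.5%. The PR size threshold is met. PR follows only if there is also measurable disease at baseline, a confirming scan 4 weeks later, the steroid limits, stable or improved T2/FLAIR, and a stable or improved clinical state. CR after complete removal also needs no steroids, with stable or improved T2/FLAIR and clinical state.

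**2. The plan's own operating characteristics (7.2)**

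P(promising) = Σ over x ≥ c1 of P(X1 = x) · P(X2 ≥ c − x), with X1 ~ Bin(n1, p) and X2 ~ Bin(n − n1, p).

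| Group | n1, c1 | n, c | p0, p1 | Error at p0 | Power at p1 | Stated |
|---|---|---|---|---|---|---|
| A | 9, 2 | 34, 9 | 15%, 35% | 4.7% | 81.1% | 5%, 80% |
| B | 14, 1 | 32, 2 | 1%, 12% | 2.9% | 80.1% | 5%, 80% |

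The stated power reproduces, and the stated 5% holds as a ceiling. No stated figure is disputed.

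**3. Sensitivity to mis-scoring.** The documents give no frequency, so f is an assumption: the share of truly progression-free patients scored as progressed. The success rate becomes p1(1 − f).

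| f | Group A rate | Group A power | Group B rate | Group B power |
|---|---|---|---|---|
| 0 | 35.00% | 81.1% | 12.00% | 80.1% |
| 1% | 34.65% | 80.1% | 11.88% | 79.7% |
| 5% | 33.25% | 76.1% | 11.40% | 77.9% |
| 10% | 31.50% | 70.1% | 10.80% | 75.4% |

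**4. One patient at the boundary.** At p1, the chance of passing stage 1 and finishing exactly on the cut-off is 6.7% in Group A (9 of 34) and 10.7% in Group B (2 of 32). In those trials one mis-scored success gives 8/34 = 23.5% instead of 26.5%, or 1/32 = 3.1% instead of 6.3%, and the conclusion reverses.

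**5. One surgical response.** 1/34 = 2.9 points (A), 1/32 = 3.1 points (B), 1/16 = 6.3 points (C). These are minimum values, because 5.2 restricts the response-evaluable set to patients with measurable disease, one cycle of therapy and a re-evaluation.

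**The case against.** The best counter-argument is that the documents, read together, already give the PFS answer. Section 4.1.8 speaks of presumed progression, 3.7.1.1 keeps patients without progression on therapy, and (b) and (d) show the same intent. A specific surgery rule would then qualify the general size threshold, and only a cross-reference is missing. This is a sensible reading, but it appears nowhere in the endpoint rules, and it does not address shrinkage caused by surgery.

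Several limits do stand.
- A reader might infer that any scan leading to such a resection is scored as progression. It is not: (b) protects a T2/FLAIR-only call and (d) a clinical-only call. The gap is confined to (a) and (c).
- A reader might infer that any resection scores as PR or CR. It does so only if the further conditions hold. Whether an excised lesion counts as assessed under 5.2.1.3 is also arguable. Response is a secondary endpoint with no decision rule in 7.2.
- The 6.7% and 10.7% might be read as chances of a reversed verdict. They are chances of finishing on the cut-off; a reversal also needs a mis-scored success.
- The event is probably uncommon. Section 2.1.1.9 generally requires at least 12 weeks since radiation, and 2.1.1.10 requires confirmed progression after brachytherapy or radiosurgery. Group B's landmark is only 3 months away. At its target rate about 32 × 0.12 = 3.8 patients are progression-free, so f = 5% is 0.19 of a patient.
- Section 2.4 lists Groups A and C as closed, so for them any rule would be written after accrual. It would still govern how their data are scored.

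**Conclusion.** The point holds in a limited form. It is a conflict between 4.1.8, 3.7.1.1 and criteria (a) and (c) of 5.2.1.3.5, together with CR, PR and best-response rules that do not address on-study surgery. The written rules can therefore give a wrong PFS status or a wrong response for an event that the plan itself anticipates.

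The expected effect is small. At f = 1% the power loss is 1.0 point or less in either group. At f = 10% it is 11.0 points in Group A (81.1 − 70.1) and 4.7 in Group B (80.1 − 75.4). These losses rest on an assumed frequency and on the design rates of 35% and 12%; the documents give no basis for choosing f. The documents do not support a claim that the trial's conclusion is likely to be wrong. They do support settling the scoring in advance: in an open-label, single-arm study with low cut-offs, it would otherwise be decided case by case with the outcome known.

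**What to change.** 1. In 5.2.1.3.5 (a) and (c), state that for endpoint scoring an enhancing increase or new lesion shown by resection pathology to be treatment-associated change only (4.1.8) is not a progression event, and that PFS follow-up continues from registration.
2. In 5.2.1.3.1, 5.2.1.3.2 and 5.2.2, state that a decrease produced by on-study resection does not count as CR or PR, and that best response for such a patient is taken from pre-operative scans.
3. Have the sponsor choose the reference scan for later progression after an on-study resection, and state it before analysis.
4. Reconcile 3.7.1.1 with 4.1.8. How treatment is handled is for the sponsor to decide; the scoring rule does not depend on it.

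**Cost.** A few sentences in section 5.2. Section 4.1.8 already requires the operative note and pathology report for surgery not due to progression, and its resumption rule cannot be applied without a pathology result.

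**Downsides.** A surgical patient cannot later be counted as a responder. If a small post-operative residual is chosen as the reference, small absolute growth counts as progression: from 1 cm² to 1.3 cm² is +30%, above the 25% threshold.

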5.0 DATA COLLECTION AND EVALUATION

5.1 DATA COLLECTION

Certain BTTC participating institutions have collected baseline data of relevance to this clinical trial including certain identifiable private information, such as patient treatment dates. For purposes of this clinical trial, these BTTC participating institutions will transfer these data to NCI through direct data entry in the NCI-designated study database (C3D) and via secure transfer through the NIH's Secure Email and File Transfer Service (SEFT) system, in accordance with their applicable laws, regulations, and policies. The BTTC Research Nurse will provide instructions to these BTTC participating institutions for use of C3D and SEFT.

The PI at the site will be responsible for overseeing entry of data into an in-house password protected electronic system and ensuring data accuracy, consistency and timeliness. The principal investigator, associate investigators/research nurses and/or a contracted data manager will assist with the data management efforts.

Data on this study will be entered into C3D and Scribe/Labmatrix. Designated research staff from the registering institution will enter the data via remote electronic data entry. The protocol specific electronic forms are to be used by the participating site. All investigators will utilize these forms for Baseline, Treatment, Adverse Events, Tumor Evaluation, Off Treatment, Survival, and Off-study data.

All data obtained during the conduct of the protocol will be kept in secure network drives or in approved alternative sites that comply with NIH security standards. Primary and final analyzed data will have identifiers so that research data can be attributed to an individual human subject participant.

All AEs, including clinically significant abnormal findings on laboratory evaluations, regardless of severity, will be followed until return to baseline or stabilization of event. Serious adverse events that occur more than 30 days after the last administration of investigational agent/intervention and have an attribution of at least possibly related to the agent/intervention should be recorded and reported as per Sections [6.3](#) and [6.5](#).

An abnormal laboratory value will be recorded in the database as an AE **only** if the laboratory abnormality is characterized by any of the following:

- Results in discontinuation from the study
- Is associated with clinical signs or symptoms
- Requires treatment or any other therapeutic intervention
- Is associated with death or another serious adverse event, including hospitalization.
- Is judged by the Investigator to be of significant clinical impact

If any abnormal laboratory result is considered clinically significant, the investigator will provide details about the action taken with respect to the test drug and about the patient's outcome.

End of study procedures: Data will be stored according to HHS, FDA regulations, and NIH Intramural Records Retention Schedule as applicable.

Loss or destruction of data: Should we become aware that a major breach in our plan to protect subject confidentiality and trial data has occurred, the IRB will be notified.

5.1.1 Source Documentation Timeframes

The following information will be entered into C3D and Scribe/Labmatrix within the indicated timeframes. In addition, the source documents should be provided to the BTTC Coordinating Center’s Research Nurse, [contact], or email within the indicated timeframe.

Data Set / Source Documents	Schedule for Submission
Regulatory Documents (as described in the BTTC Operations Manual)	Prior to Patient Registration
Eligibility Checklist	Prior to Patient Registration
Copy of signed & dated Informed Consent w/ HIPAA Authorization	Prior to Patient Registration
Pathology Report (from the most recent pre- registration diagnostic biopsy or surgery)	Prior to registration
Baseline Data (To include prior disease/treatment history, and baseline clinical evaluation information)	Within 14 days after the registration date
Baseline MDASI – BT Questionnaire	Within 14 days after the registration date
Baseline Source Documents	Within 14 days after the registration date

5.1.2 Database Entry Timeframes

The following data should be entered into C3D/Labmatrix within the specified timeframes. Source documentation will be kept at the participating site.

Treatment (Cycle) Data (To include treatment, response, AE, and clinical evaluation information)	Within 40 days after the first day of each treatment cycle.
Off Treatment Data	Within 10 days after the last date of any modality of protocol treatment
Follow-up (Survival) Data	Within 52 days after the last treatment date and then every 90 days until Off Study (unless otherwise specified by the protocol)
Non-Treatment Data (May include Quality of Life questionnaires (MDASI-BT), Specimen Tracking information, Pathology Specimen Submission, etc.)	Within 10 days after each scheduled assessment, event, or activity
Off Study Data	Within 10 days after the date the patient is removed from the study.

5.1.3 Confidentiality

All documents, investigative reports, or information relating to the patient are strictly confidential. Any patient specific reports (i.e. Pathology Reports, MRI Reports, Operative Reports, etc.) submitted to the BTTC Coordinating Center must have the patient's full name & social security number "blacked out" and the assigned patient ID number and protocol number written in. Patient initials may be included or retained for cross verification of identification.

5.1.4 Safety Data

All patients receiving study agents will be evaluated for safety. The safety parameters include all laboratory tests and hematological abnormalities, CNS observations, physical examination findings, and spontaneous reports of adverse events reported to the investigator by patients. All toxicities encountered during the study will be evaluated according to the NCI Common Terminology Criteria for Adverse Events (CTCAE) version 4.0 and recorded prior to each course of therapy. Life-threatening toxicities that are unexpected and assessed to be possibly related to the study agent/s should be reported immediately as per Section 6.5.

Information about all adverse events, whether volunteered by the subject, discovered by investigator questioning, or detected through physical examination, laboratory test or other means, will be collected and recorded on the Adverse Event Case Report Form and followed as appropriate. An adverse event is any undesirable sign, symptom or medical condition occurring after starting study drug (or therapy) even if the event is not considered to be related to study drug.

Medical conditions/diseases present before starting study treatment are only considered adverse events if they worsen after starting study treatment (any procedures specified in the protocol). Adverse events occurring before starting study treatment but after signing the informed consent form are recorded on the Baseline Evaluations Case Report Form. Abnormal laboratory values or test results constitute adverse events only if they induce clinical signs or symptoms or require therapy, and are also recorded on the Adverse Events Case Report Form.

5.1.5 Data Sharing with Pharmaceutical Collaborators, Bayer and Novartis

NCI may share data from this study with pharmaceutical collaborators, Bayer and Novartis, pursuant to the NCI M-CRADAs with each company. Specifically, the collaborators may access and review analytical results and primary quantitative and empirical data including identifiable private information in accordance with the terms of the M-CRADAs.

